Duration of Treatment:

Each treatment cycle will be 28 days of twice daily dosing. Treatment will continue until the subject experiences unacceptable drug-related intolerability.

Once the requisite number of events has occurred and the blind is opened for analysis of the trial results, any surviving subjects who remain on blinded drug will be offered the opportunity to continue dosing with open-label CF102 25 mg BID indefinitely, following the protocol-specified schedule of events ([Table 1–2](#)).

Criteria for Evaluation:

Efficacy:

The primary efficacy endpoint will be OS, defined as the number of days from first dose to death due to any cause. Secondary endpoints to be evaluated are TTP, PFS, OR rate consisting of Complete Response (CR) or Partial Response (PR) for subjects who enter the trial with measurable disease by RECIST v1.1, and DC rate which includes both subjects who experience OR as well as those who experience Stable Disease (SD). Survival status will be assessed continuously. Tumor status will be assessed at the Pre-Study Visit and every 8 weeks thereafter (i.e., at the end of even-numbered cycles) by computed tomography (CT) scan or magnetic resonance imaging (MRI) according to RECIST v1.1 ([Appendix A](#), [Eisenhauer 2009 as modified by Santoro 2013]).

Alpha-fetoprotein (AFP) levels will be assessed at baseline and every 4 weeks thereafter on Day 1 of each subsequent cycle.

Laboratory parameters associated with hepatic dysfunction and cirrhosis, such as serum ALT, AST, bilirubin, and albumin levels, prothrombin time (PT), and International Normalized Ratio (INR), will be assessed every cycle. Where applicable, viral load measurements will be performed every odd-numbered cycle. WBC A₃AR expression will be assessed at baseline and, unless waived by the Sponsor, every odd-numbered cycle (at selected sites only).

Safety:

Assessments of adverse events (AEs) will include characterization of the type, incidence, severity (graded by CTCAE v 4.0), seriousness, and relationship to treatment. Changes in vital signs, laboratory parameters including thyroid functions, electrocardiograms (ECG), physical examinations, and ECOG PS from baseline will be assessed.

Pharmacokinetics:

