12.2 Sample Size Determination

Approximately 78 subjects will be enrolled and randomized to either CF102 or placebo using a 2:1 randomization. The post-accrual treatment period was originally planned to continue until a total of 75 deaths have been recorded. Assuming a hazard ratio of 0.5, 75 events will provide 80% power for the logrank test at level 0.05 (two-sided). It is assumed that the 78 subjects will be enrolled in approximately 78 weeks and the trial will continue for a total of 104 weeks (SiZ: Logrank Test with Given Accrual Duration and Study Duration, Version 2.0, Cytel, Inc. 2011). The required number of deaths and the required number of subjects are reasonably stable with respect to the duration of accrual and length of the post-accrual follow-up period, being between 70 and 80, to have power of 80% for an assumed hazard rate of 0.5, especially for studies with a post-accrual follow-up period.

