#### 3. SAMPLE SIZE, RANDOMIZATION AND BLINDING

#### 3.1 SAMPLE SIZE

Approximately 78 subjects will be enrolled during an accrual period estimated to be approximately 102 weeks (24 months) in duration and randomized to either CF102 or placebo using a 2:1 randomization. The post-accrual treatment period will continue until a total of 75 subjects have died. Assuming a hazard ratio of 0.5, 75 deaths will provide 80% power for the logrank test at level 0.05 (EAST 6, Cytel, 2014).

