#### 7.7.1 ADVERSE EVENTS

The original reported (verbatim) terms used by the Investigator to identify adverse events in the CRFs will be entered into the database and coded by Preferred Term using the Medical Dictionary for Regulatory Activities (MedDRA) coding dictionary (MedDRA MSSO, Reston, Virginia USA). Adverse events will then be grouped by MedDRA Preferred Term (PT) into frequency tables according to System Organ Classification (SOC).

An adverse event that started during the treatment period (on or after the day of the baseline visit) or that was present at Baseline and increased in severity during the treatment period will be considered a treatment-emergent adverse event (TEAE). Events ending prior to the day of the baseline visit and events present at Baseline that do not increase in severity during treatment will be considered as Baseline adverse events and will not be included in the presentation of TEAEs. If the date of a new AE does not allow for determination of whether the AE is treatment emergent, it will be assumed to be a TEAE.

The number and percentage of subjects experiencing TEAEs will be presented for the Safety Population for each body system and preferred term by treatment, and for each severity and relationship to study medication. When an adverse event occurs more than once, the maximum severity grade and relationship will be counted. For severity, only "Mild" and "Moderate" will be included for all SOCs and PTs; "Severe", "Life-Threatening", or "Fatal" will be included for SOCs and PTs only when such are recorded for severity. Similarly, only "Possibly Related" and "Not Related" will be included for all SOCs and PTs; "Definitely Related" and "Probably Related" will be included for SOCs and PTs when such are recorded for relationship.

Serious adverse events and discontinuations due to an adverse event will be provided in separate listings for the Safety Population. Each serious adverse event (SAE) will be listed for subjects in the Safety Population.

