Overall Survival (OS; months) by Country ITT Population

		CF102	Placebo
Country	Statistic	(N=xx)	(N=xx)
Bulgaria	n	XX	XX
	25th Percentile	XX.X	XX.X
	Median	XX.X	XX.X
	75th Percentile	XX.X	XX.X
	Number (%) observed events	xx (xx.x)	xx (xx.x)
	Number (%) censored	xx (xx.x)	xx (xx.x)
	P-value (LR)	0.xxx	
	HR	X.XX	
	95% CI for HR	(x.xx, x.xx)	
	P-value (PH)	0.xxx	
Israel	n ` ´	XX	XX
	25th Percentile	XX.X	XX.X
	Median	XX.X	XX.X
	75th Percentile	XX.X	XX.X
	Number (%) observed events	xx (xx.x)	xx (xx.x)
	Number (%) censored	xx (xx.x)	xx (xx.x)
	P-value (LR)	0.xxx	
	HR `´	X.XX	
	95% CI for HR	(x.xx, x.xx)	
	P-value (PH)	0.xxx	

P-value (LR) =P-value using the logrank test.

Percentages are calculated using the number of subjects in the ITT Population in the specified subgroup category for each treatment as the denominator.

HR=Hazard Ratio for Treatment from Proportional Hazards Model with Treatment as the only factor in the model and P-value (PH) is the corresponding p-value (Chi-Square).

Source: Listings 16.2.1.1, 16.2.5.1

Programming Note: Continue for each country (Bulgaria, Israel, Romania, Serbia, or United States) alphabetically.

Table 14.3.1 Incidence of Treatment-Emergent Adverse Events Safety Population

MedDRA System Organ Class	MedDRA Preferred Term, n (%)	CF102 (N=xx)	Placebo (N=xx)
Any	Any	xx (xx.x)	xx (xx.x)
Body as a Whole	Any	xx (xx.x)	xx (xx.x)
	Fever	xx (xx.x)	xx (xx.x)

All AEs in this table are treatment emergent. Percentages are calculated using the number of subjects in the Safety Population for each treatment as the denominator.

MedDRA version: 21.0 Source: Listing 16.2.7

Programming Note: Continue for all SOCs and Preferred Terms.

Table 14.3.2 Incidence of Treatment-Emergent Adverse Events by Relationship Safety Population

MedDRA System Organ Class	MedDRA Preferred Term	Relationship, n (%)	CF102 (N=xx)	Placebo (N=xx)
			, ,	, ,
Any	Any	Definitely Related	xx (xx.x)	xx (xx.x)
		Probably Related	xx (xx.x)	xx (xx.x)
		Possibly Related	xx (xx.x)	xx (xx.x)
		Not Related	xx (xx.x)	xx (xx.x)
Body as a Whole	Any	Definitely Related	xx (xx.x)	xx (xx.x)
•	-	Probably Related	xx (xx.x)	xx (xx.x)
		Possibly Related	xx (xx.x)	xx (xx.x)
		Not Related	xx (xx.x)	xx (xx.x)
	Fever	Definitely Related	xx (xx.x)	xx (xx.x)
		Probably Related	xx (xx.x)	xx (xx.x)
		Possibly Related	xx (xx.x)	xx (xx.x)
		Not Related	xx (xx.x)	xx (xx.x)

All AEs in this table are treatment emergent.

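### Adverse events are tabulated only as crude percentages of dosed subjects although dosing is open-ended, so a survival difference between arms would distort the safety comparison

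*SAP*

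**What the plan says.** **Adverse event measure.** SAP 7.7.1 states that "The number and percentage of subjects experiencing TEAEs will be presented for the Safety Population for each body system and preferred term by treatment", with the same counts split by severity and by relationship. The footnote to Tables 14.3.1 to 14.3.3 reads "Percentages are calculated using the number of subjects in the Safety Population for each treatment as the denominator". Serious events and discontinuations due to adverse events are listed, not tabulated (Tables 14.3.4.2 and 14.3.5). Neither document plans a between-arm test of adverse events.

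**Counting window.** SAP 7.7.1 ties treatment emergence to the subject's own treatment period. Protocol 9.2.4 collects events up to the visit 28 days after the last dose.

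**End of dosing.** The protocol synopsis says: "Treatment will continue until the subject experiences unacceptable drug-related intolerability". Under Protocol 9.2.12, documented progression does not take a subject off the trial. Protocol 7.4 and SAP 4.3 also end dosing for consent withdrawal, investigator discretion, intercurrent illness, an interruption of more than 14 days unrelated to toxicity, noncompliance, pregnancy and sponsor termination. No rate is given for any of these.

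**Exposure.** SAP 7.5.1 and Table 14.1.7 summarise duration of treatment by arm. Nothing links that summary to the adverse event tables.

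**The concern.** The proportion of subjects with at least one event depends on the event rate and on how long each subject is observed. Here the observation time is not fixed, and the trial is powered for a large survival difference, so unequal time at risk is the planned scenario. If CF102 prolongs survival, its percentages rise with no added toxicity. If it shortens survival, real toxicity is understated. Tables 14.3.2 and 14.3.3, which count each subject's strongest relationship and highest severity, carry the same distortion.

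Characterising safety is a stated secondary objective, and SAP 2.2 says the trial evaluates safety as compared to placebo. The two-column percentages are what a reader will use for that.

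**Working it through.** **Inputs from the documents.** SAP 3.1: "Assuming a hazard ratio of 0.5, 75 deaths will provide 80% power for the logrank test at level 0.05". Protocol 12.2 adds that the level is two-sided. Subjects are "randomized to either CF102 or placebo using a 2:1 randomization", so about 52 and 26 of 78. Follow-up: "The post-accrual treatment period will continue until a total of 75 subjects have died" (SAP 3.1), against "the 78 subjects will be enrolled in approximately 78 weeks and the trial will continue for a total of 104 weeks" (Protocol 12.2). Protocol 4.5.2 gives median survival of at most about 2 months after sorafenib failure, and 3.5 to 5.5 months for Child-Pugh B patients in general.

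**Assumptions.** The documents give no placebo adverse event incidence. I take event hazards of 0.02 to 0.20 per month, constant and equal in both arms, and exponential survival.

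**1. The plan's own figure.** Schoenfeld events at 2:1: (1.960 + 0.842)² / [(2/3)(1/3)(ln 0.5)²] = 7.85 / 0.1068 = 73.5, so 74 deaths. Power at 75 deaths is 80.8%. The stated 75 deaths and 80% reproduce, so 0.5 is a fair planning value to carry forward.

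**2. Death as the only end of dosing, no cut-off.** With event hazard a and placebo death hazard m = ln 2 / median:

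- placebo incidence p0 = a/(a + m)
- CF102 incidence p1 = a/(a + 0.5m)
- crude ratio p1/p0 = 2/(1 + p0)

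Example at a placebo median of 3.5 months (m = 0.198) and a = 0.10: p0 = 0.10/0.298 = 33.6%, p1 = 0.10/0.199 = 50.2%, ratio 1.50.

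- Median 2 months, a = 0.02: p0 = 5.5%, ratio 1.90.
- Median 5.5 months, a = 0.20: p0 = 61.3%, ratio 1.24.
- Assumed incidence of 90% to 95%, as an any-event row might show: ratio 1.05 to 1.03.

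**3. Other reasons for stopping.** Add a non-death stopping hazard f·m, equal in both arms. The ratio becomes 1/[p0 + r(1 − p0)], with r = (0.5 + f)/(1 + f).

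| Placebo dosing ending other than by death | r | Ratio at p0 = 5% | Ratio at p0 = 61% |
|---|---|---|---|
| 0% | 0.50 | 1.90 | 1.24 |
| 20% | 0.60 | 1.61 | 1.18 |
| 33% | 0.67 | 1.46 | 1.15 |
| 50% | 0.75 | 1.31 | 1.11 |

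**4. Cut-off at 104 weeks.** With follow-up spread evenly over 6 to 24 months and no other discontinuation, the ratio for a term near 5% is 1.77, 1.59 or 1.44 at placebo medians of 2, 3.5 or 5.5 months. For a term near 67% it stays at about 1.2. If the trial instead runs until 75 of about 78 have died, truncation is slight.

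**5. Would rates alone solve it?** With a constant hazard, events per person-time give a ratio of 1.0. Now let events arise only in the first 2 months, at 0.10 per month in both arms, with a placebo median of 3.5 months.

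- Incidence: placebo 0.336 × (1 − e^−0.596) = 15.1%; CF102 0.502 × (1 − e^−0.398) = 16.5%. Crude ratio 1.10.
- Mean time at risk to first event or death: placebo 0.449/0.298 + 0.551/0.198 = 4.29 months; CF102 0.328/0.199 + 0.672/0.099 = 8.43 months.
- Rate ratio: (0.165/8.43)/(0.151/4.29) = 0.56.

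Equal toxicity would look like a 44% reduction on CF102. Rates help for events spread over time and mislead for early ones.

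**The case against.** The strongest reply is that these tables are descriptive, exposure is already reported by arm, and the size of the bias rests on chosen inputs.

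Much of this stands. There is no adverse event test, so nothing is formally compared. The event hazards have no source in the documents and they set the answer. Time on drug drives the bias rather than survival itself, and the several other stopping reasons weaken the link between the two. With about 52 and 26 subjects, rates for rare terms would be very imprecise. The SAP already records decisions taken after unblinding (7.6.8 and Section 9), so a new basis for safety conclusions would be post hoc.

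It does not remove the point. Side-by-side percentages are read as a comparison whether or not a p-value is attached. Table 14.1.7 tells the reader that exposure differs but cannot correct any row. The other stopping reasons shrink the excess without abolishing it.

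A reader might also infer that an inert drug would show a 1.2- to 1.9-fold excess. The documents do not support that. An inert drug has a hazard ratio of 1 and shows no excess; the relevant case is a drug that prolongs survival and causes no adverse events. Nor does a hazard ratio of 0.5 by itself double time on drug. That requires nearly all dosing to end by death.

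**Conclusion.** The point holds as a gap in the safety summaries. Crude percentages are the only tabulated measure, dosing is open-ended, and no planned output adjusts for time at risk. The 1.2 to 1.9 range is an upper range, not a prediction. It rests on a hazard ratio of 0.5, constant and equal event hazards, an assumed placebo incidence of about 5% to 61%, death as the sole end of dosing, and no data cut-off. Relaxing the last two reduces it, and the direction reverses if CF102 shortens survival.

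A reader might go further and conclude that safety statements should rest on exposure-adjusted rates. The early-onset example shows why they should not. The primary survival test is unaffected, and the change is a cheap improvement.

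**What to change.** Keep the crude percentages in Tables 14.3.1 to 14.3.3. Add a supplementary summary, labelled as a late addition:

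- First-event rates per 100 subject-months by arm with 95% confidence intervals, for Grade 3 or higher, serious and related treatment-emergent events and for the more common preferred terms. Time at risk runs from first dose to the first event or the end of the same window that defines treatment emergence.
- A fixed early-window summary, for example the first two cycles, or a time-to-first-event summary, because the rates assume a roughly constant hazard.
- A sentence in SAP 7.7.1 stating that between-arm safety differences are interpreted from these summaries together with the percentages and Table 14.1.7, not from the rates alone.

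**Cost.** First- and final-dose timing is in Listing 16.2.4.1 and event start dates are in Listing 16.2.7, so no new data are needed. The tables become wider and the rates will be imprecise at this sample size. SAP Section 8 imputes only the final-dose date, so a simple rule for partial onset dates must be added. The SAP must also state whether the window ends at the last dose or includes the 28-day follow-up.

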4.5 Potential Risks and Benefits of Therapy

4.5.1 Risks

Adverse events observed during CF102 therapy in the CF102-102HCC trial included the following:

- Most common AEs (4 or more occurrences, all causalities combined): abdominal pain, ascites, diarrhea, edema, fatigue, fever, lack of appetite, pain, and weakness.
- AEs considered possibly or probably related to CF102: pain in various bodily locations, fatigue, diarrhea, lack of appetite, weakness, and fever.
- Of the 25 serious adverse events reported, ascites, cellulitis, cerebral hemorrhage, headache, hyponatremia, and leg thrombus were considered at least possibly related to CF102.

For additional information, please refer to the Investigator Brochure.

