12.4.3 Safety Data

Safety observations and measurements including study drug exposure, adverse events, laboratory data, physical examination findings, vital signs, ECG, and ECOG PS will be summarized and presented in tables and listings.

Laboratory parameters including thyroid functions will be summarized using descriptive statistics and data listings of clinically significant abnormalities. Physical examinations, vital signs, ECOG PS, and ECG data will be summarized by changes from baseline values for each treatment using descriptive statistics. Liver Chemistry Tests, INR, and viral load will be presented as exploratory efficacy variables.

Adverse events will be coded using the MedDRA™ dictionary. The number and percentages of subjects experiencing AEs will be tabulated by system organ class and preferred term. Assessments of AEs will include characterization of the type, incidence, severity, seriousness, and relationship to treatment. Summary subject listings will be provided for subjects with dose interruptions and dose reductions, SAEs, AEs resulting in discontinuation from the trial, and deaths. Adverse events will be graded according to NCI-CTCAE criteria, version 4.0.

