#### 7.7 SAFETY ANALYSES

Safety data consist of adverse events (AEs), laboratory tests including thyroid functions, vital signs and weight, and physical examinations. Summaries of safety data will be conducted on all subjects in the Safety Population. Missing safety data will not be imputed. Summaries of all safety variables by visit will be presented for visits at which there are at least 4 subjects in either treatment group. Summaries of AEs, deaths, SAEs, and Discontinuation due to AE will not be restricted to visits with at least 4 subjects in either treatment group. All safety data will be listed.

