14.2.5.3	Albumin	ITT	16.2.8.2	
14.2.5.4	Bilirubin (direct)	ITT	16.2.8.2	
14.2.5.5	Bilirubin (total)	ITT	16.2.8.2	
14.2.5.6	International Normalized Ratio (INR)	ITT	16.2.8.3	
14.2.5.7	Prothrombin time (PT)	ITT	16.2.8.3	
14.2.6	Hepatitis Viral Load	ITT	16.2.3.3.1,	
			16.2.6.5.1 , 16.2.6.5.2	
	SUBGOUP ANALYSES - EFFICACY			
14.2.7.1	Overall Survival (OS; months) by Child-Pugh (CP) Score at Screening	ITT	16.2.3.1, 16.2.5.1	
	Figure 14.2.7.1: Kaplan-Meier curve for OS, CP Score at Screening = 7	itt	16.2.3.1 , 16.2.5.1	
	Figure 14.2.7.2: Kaplan-Meier curve for OS, CP Score at Screening = 8	ITT	16.2.3.1, 16.2.5.1	
	Figure 14.2.7.3: Kaplan-Meier curve for OS, CP Score at Screening = 7 or 8	ITT	16.2.3.1, 16.2.5.1	
14.2.7.2	Overall Survival (OS; months) by Sex	ITT	16.2.3.1, 16.2.5.1	
14.2.7.3	Overall Survival (OS; months) by ECOG PS at Screening	ITT	16.2.9.3 , 16.2.5.1	
14.2.7.4	Overall Survival (OS; months) by Alpha-fetoprotein (AFP) at Baseline	ITT	16.2.6.4, 16.2.5.1	
14.2.7.5	Overall Survival (OS; months) by Prior Locoregional Therapy	ITT	16.2.3.4 , 16.2.5.1	
14.2.7.6	Overall Survival (OS; months) by Either EHS or PVT	ITT	16.2.3.3.2, 16.2.5.1	
14.2.7.7	Overall Survival (OS; months) by History of HBV	ITT	16.2.3.3.1, 16.2.5.1	
14.2.7.8	Overall Survival (OS; months) by History of HCV	ITT	16.2.3.3.1, 16.2.5.1	
14.2.7.9	Overall Survival (OS; months) by Diagnostic Procedure	ITT	16.2.3.2, 16.2.5.1	
14.2.7.10	Overall Survival (OS; months) by Country	ITT	16.2.1.1, 16.2.5.1	
	THE PREVIOUS SHOULD BE IN THE SAME ORDER AS IN TEXT			
	SAFETY			
	Adverse Events			
14.3.1	Incidence of Treatment-Emergent Adverse Events	Safety	16.2.7	
14.3.2	Incidence of Treatment-Emergent Adverse Events by Relationship	Safety	16.2.7	
14.3.3	Incidence of Treatment-Emergent Adverse Events by Severity	Safety	16.2.7	
14.3.4.1	Listing of Deaths	Safety	16.2.1.1 , 16.2.5.1 ,	
		23.00,	16.2.7	
14.3.4.2	Listing of Serious Adverse Events	Safety	16.2.7	
14.3.5	Listing of Discontinuations due to Adverse Events	Safety	16.2.7	

Title of Table	Population	Listing Source
Laboratory Values		
• • • • • • • • • • • • • • • • • • •	Cofot.	40.0.0.4
	•	16.2.8.1
	Safety	16.2.8.2
Clinical Laboratory Evaluations: Coagulation	Safety	16.2.8.3
Clinical Laboratory Evaluations: Thyroid Function	Safety	16.2.8.5
Other Safety		
ECOG Performance Status (PS)	Safety	16.2.9.3
	•	16.2.9.3
	•	16.2.9.1, 16.2.9.2
	,	16.2.10.1

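### No planned table gives, by arm, the subjects with an SAE, with a related SAE, or with a single event that is both Grade 3 or higher and at least possibly related

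*SAP*

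**What the plan says.** **SAEs.** SAP 7.7.1 plans listings: "Serious adverse events and discontinuations due to an adverse event will be provided in separate listings for the Safety Population". The output list in the shells agrees. Table 14.3.4.2 is titled "Listing of Serious Adverse Events" and shows treatment, grade, relationship, action taken and outcome for each event. No output in the 14.3 series counts subjects with an SAE.

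**All TEAEs.** SAP 7.7.1 states: "The number and percentage of subjects experiencing TEAEs will be presented for the Safety Population for each body system and preferred term by treatment", with further breakdowns by severity and by relationship. The rule for repeat events is: "When an adverse event occurs more than once, the maximum severity grade and relationship will be counted". Table 14.3.1 gives overall incidence, 14.3.2 the most related event per subject and term, and 14.3.3 the most severe. None crosses severity with relationship.

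**Statements elsewhere.** SAP 7.7 speaks of summaries: "Summaries of AEs, deaths, SAEs, and Discontinuation due to AE will not be restricted to visits with at least 4 subjects". Protocol 12.4.3 says: "Assessments of AEs will include characterization of the type, incidence, severity, seriousness, and relationship to treatment". The same protocol section, and the synopsis, then plan subject listings for SAEs.

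**Withdrawals.** Table 14.1.2 gives n (%) by arm for primary reasons for withdrawal from dosing. One row is for at-least-possibly-related Grade 3 toxicity not resolved within 7 days and another for at-least-possibly-related Grade 4 toxicity.

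**The concern.** Characterising the safety of CF102 is a stated secondary objective, and the protocol describes the earlier HCC trial partly in terms of serious and drug-related events. Section 4.5.1 begins "Of the 25 serious adverse events reported" and goes on to name those thought at least possibly related to CF102. Section 4.2.2 names the Grade 3 drug-related events and one possibly related death. A reader of the new trial will look for the same quantities compared between arms and will find no table that gives them.

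A listing is an awkward substitute here. Allocation is 2:1, so row counts cannot be compared without dividing by each arm's N. One subject can contribute several rows. Protocol 11.5.1 makes deaths within 30 days of the last dose SAEs, and treatment may continue after progression, so the SAE listing is likely to mix many disease deaths with the events of interest. Each reader would have to remove duplicate subjects, separate related from unrelated events and supply the denominators.

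**Working it through.** The plan states no figure on this point, so the check traces the outputs and then asks what the two TEAE tables can determine.

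**1. Outputs against the quantities needed**

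| Quantity by arm | Where it could come from | Given as n (%)? |
|---|---|---|
| Subjects with any SAE | 14.3.4.2 and 16.2.7, both listings | No |
| Subjects with a related SAE | Same listings | No |
| Subjects with any Grade 3 or higher TEAE | 14.3.3, upper grades of the Any row | Yes |
| Subjects with any related TEAE | 14.3.2, related categories of the Any row | Yes |
| Subjects with one event both Grade 3 or higher and related | 14.3.2 and 14.3.3 do not cross the two | No |
| Withdrawal from dosing for related unresolved Grade 3 or related Grade 4 toxicity | 14.1.2 | Yes, primary reason only |

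**2. Why the two TEAE tables do not give the joint count**

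Take subject A with unrelated Grade 3 fatigue and a separate, possibly related Grade 1 fatigue. Take subject B with one possibly related Grade 3 fatigue. Under the rule that "the maximum severity grade and relationship will be counted", both appear as Severe in Table 14.3.3 and as Possibly Related in Table 14.3.2. Only B has a related Grade 3 event.

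Let a be the number of subjects with a Grade 3 or higher event and b the number with a related event in the same row. The number with one event that is both lies between 0 and min(a, b). Preferred-term rows can lower that ceiling. They cannot raise the floor above 0, because no table counts repeat occurrences.

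**3. Illustration**

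Inputs: about 78 subjects at 2:1 (synopsis, SAP 3.1), so 78 × 2/3 = 52 on CF102 and 26 on placebo. The percentages with a Grade 3 or higher event and with a related event are assumptions, since the documents give none.

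| Assumed Grade 3+ / related | CF102 (52): a, b | Joint range | Placebo (26): a, b | Joint range |
|---|---|---|---|---|
| 30% / 20% | 16, 10 | 0 to 10 (19.2%) | 8, 5 | 0 to 5 (19.2%) |
| 50% / 30% | 26, 16 | 0 to 16 (30.8%) | 13, 8 | 0 to 8 (30.8%) |
| 60% / 40% | 31, 21 | 0 to 21 (40.4%) | 16, 10 | 0 to 10 (38.5%) |

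The two arms could sit at opposite ends of these ranges without any change in the overall rows of either table.

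**4. What Table 14.1.2 adds and leaves out**

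Its two toxicity rows do combine grade and relationship. They count only subjects for whom that was the recorded primary reason for stopping study drug. A programming note says a subject should have a reason for withdrawal from dosing or from the trial, not both, so a subject recorded under death would not appear in the toxicity rows. Related Grade 3 events that resolve within 7 days of interruption do not appear there either. SAP section 9 drops the listing of interruptions and reductions that the protocol promised and refers to the action-taken field. The codes shown for that field cover delay and discontinuation but not reduction.

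**The case against.** The strongest reply is that the SAP does what the protocol set out. Protocol 12.4.3 and the synopsis plan subject listings for SAEs, and the SAP supplies them. The reference to summaries in SAP 7.7 only exempts certain outputs from the four-subject visit limit; section 9 restates it that way. On this reading it is loose wording and not a promised table left out. That largely stands. The mismatch between 7.7 and 7.7.1 needs tidying, but it is not a departure from the protocol.

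A reader might infer that these quantities are never reported. The documents do not support that. Listing 16.2.7 shows arm, grade, relationship and seriousness for every event, Table 14.1.1 gives the denominators, and with about 78 subjects the counts can be made by hand. They are untabulated, not unavailable.

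A reader might also take a related Grade 3 event to be what ends dosing. Under Protocol 8.2 and SAP 2.4 it first leads to interruption. Dosing ends if the event does not resolve to Grade 1 or lower within 7 days, or if Grade 3 or 4 related toxicity occurs on rechallenge. A related Grade 4 event ends it directly. Table 14.1.2 has rows for the unresolved Grade 3 and the Grade 4 cases, which is real partial cover.

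Finally, one could scale the earlier trial's 25 SAEs in 19 subjects to the two arms and present the excess of CF102 rows as the size of the problem. That only returns the 2:1 allocation. It also borrows an event rate from an open-label trial at 1, 5 and 25 mg BID in Child-Pugh A and B subjects. It says nothing about how many subjects are affected.

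**Conclusion.** The point holds as a gap in tabulation. Three figures by arm are missing from the planned tables: subjects with any SAE, subjects with an at-least-possibly-related SAE, and subjects with one event that is itself Grade 3 or higher and at least possibly related. The first two appear only as listing rows. The third cannot be recovered from Tables 14.3.2 and 14.3.3. Table 14.1.2 narrows the gap but does not close it, because it rests on primary reasons for withdrawal and misses related Grade 3 events that resolved after interruption.

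The size cannot be stated from the documents. Under the assumed percentages above, the overall rows leave the joint count for CF102 undetermined over a range of 19 to 40 percentage points. The conclusion itself does not rest on those percentages; it follows from maximising grade and relationship separately. The primary analysis is unaffected. This is a worthwhile, low-cost improvement to safety reporting.

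**What to change.** Add to the 14.3 series, for the Safety Population, n (%) of subjects by arm, overall and by SOC and preferred term, with:

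- (a) at least one SAE;
- (b) at least one SAE that is at least possibly related;
- (c) at least one TEAE that is itself Grade 3 or higher and at least possibly related, with both criteria applied to the same event before subjects are counted.

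A risk difference with a confidence interval on the overall row is optional; the plan's AE tables are otherwise descriptive.

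In SAP 7.7, either refer to these new tables where SAE summaries are mentioned or change the wording to match the listings in 7.7.1. Record the addition in SAP section 9 or the clinical study report. Because this SAP version already contains decisions made after unblinding, label the tables as added at that stage.

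The cost is a little extra programming. All the fields needed are in Listing 16.2.7, and no data collection or dosing rule changes.
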